17.4.1. VITAL SIGNS MARKEDLY ABNORMAL CRITERIA

MAPVS measurements will be identified in accordance with the following predefined markedly abnormal criteria:

Table 5. Markedly abnormal vital sign criteria.

Parameter Name	Low	Decrease from Baseline	High	Increase from Baseline
Systolic BP	≤ 90 mmHg	≥ 20 mmHg	≥ 180 mmHg	≥ 20 mmHg
Diastolic BP	≤ 50 mmHg	≥ 15 mmHg	≥ 105 mmHg	≥ 15 mmHg
Pulse rate	≤ 50 bpm	≥ 15 bpm	≥ 120 bpm	≥ 15 bpm
Respiration Rate	≤ 10 breaths/min	$\geq 50\%$	≥ 25 breaths/min	$\geq 50\%$
Temperature	N/A		≥ 38.3 °C	≥ 0.8 °C increase from baseline

Note: A vital sign measurement is MAPVS Low if it is below the specified lower limit and decreased from baseline or MAPVS High if it is above the specified upper limit and increased from baseline.

Document:

Author:

Version Number:

V2.0

Version Date:

21MAY2020

Template No: CS_TP_BS016 Revision 4
 Effective Date: 01Apr2016

Reference: CS_WI_BS005

17.5. PHYSICAL AND NEUROLOGICAL EXAMINATION

As all physical and neurological findings will be recoded as medical history or AEs, no specific analysis of physical and neurological examination will be performed.

17.6. OTHER SAFETY ASSESSMENTS

17.6.1. TREATMENT-EMERGENT MANIA – YOUNG MANIA RATING SCALE (YMRS)

The YMRS is an 11-item instrument used to assess the severity of mania in patients with a diagnosis of bipolar disorder (see [Section 16.3.1.7](#) for details). Number and percentage of patients with treatment-emergent mania, as assessed by the YMRS total score of ≥ 16 on any 2 consecutive visits or at the last YMRS assessment, or an AE of mania or hypomania as assessed by medical review will be summarized by treatment group for the SAF population. For incidence summaries, each subject will be counted only once if multiple criteria are met. Mania incidence rates will be analyzed for the SAF population similarly to the MADRS responder analysis. The mania indicator will be set to 1 if the subject exhibits postbaseline mania, 0 if the subject does not experience post-baseline mania and has at least 1 non-missing postbaseline YMRS total score, and to missing if there is no postbaseline YMRS total score.

The change from baseline over time in the YMRS total score will also be analyzed for the ITT population using the ANCOVA and MMRM method as described in the efficacy section ([Sections 16.3.1.7](#) and [16.3.3.7](#)).

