15.3.6.2. Treatment-Emergent Mania

Number and percentage of patients with treatment-emergent mania, as assessed by the YMRS total score of ≥ 16 on any 2 consecutive visits or at the final assessment, or an AE of mania or hypomania will be summarized by treatment group. Mania incidence rates will be analyzed similarly to the MADRS responder analysis. The mania indicator will be set to 1 if the subject exhibits post-baseline mania, and 0 if the subject does not experience post-baseline mania and has at least 1 non-missing post-baseline YMRS total score, and missing otherwise.

The change from baseline in the YMRS total score will also be analyzed using the MMRM method described above for the primary efficacy variable and appropriate baseline as a covariate.

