In addition, the following composite variables will be summarized: days = 0 at baseline, days at Week 6 ≥ 1 ; days ≥ 1 at baseline, days at Week 6 = 0; days = 0 at baseline, days at Week 6 ≥ 3 ; days ≥ 3 at baseline, days at Week 6 = 0. Results for these composite variables will be evaluated using logistic regression utilizing a 0-1 indicator (1 = met the criteria, 0 = did not meet the criteria) as the dependent variable, treatment and region as categorical factors, and baseline SDS total score as a covariate. If the model fails to converge, the model will be attempted without region first, and if still not converging then without baseline SDS total score. Contrasts will be evaluated for each treatment group compared to placebo. Odds Ratios, 95% CIs and Wald chi-square p-values will be presented for each contrast. Only n and percent will be presented in cases where the number of subjects meeting the above composite variable criteria is too small for an analysis to be performed. A Cochran-Armitage trend test will also be conducted on this outcome across placebo and the treatment groups.

16.3.3.4. Change from baseline in EQ-5D-5L Scores at Week 6

The EQ dimension scores, VAS score, and index score and change from baseline will be summarized by time point for each treatment group. Change from baseline of EQ VAS and index score at Week 6 will be analyzed by the ANCOVA model described in [Section 16.1.5.1](#) with baseline EQ VAS and baseline index score as a covariate, respectively.

16.3.3.5. MADRS responders at Week 6

For MADRS responder, any ITT subject with missing response at Week 6 will be classified as Non-responder. As a sensitivity analysis, the same analysis will be repeated by only using observed values and not including subjects with missing responses. This sensitivity analysis will be repeated by removing remote visits due to COVID-19.

Document:

Author:

Version Number:

V2.0

Version Date:

21MAY2020

Template No: CS_TP_BS016 Revision 4
Effective Date: 01Apr2016

Reference: CS_WI_BS005

The MADRS total score responder proportions at Week 6 will be compared among the 3 treatment groups using logistic regression. This model will include treatment and region as fixed effects and baseline MADRS score as a covariate. If the model fails to converge, the model will be attempted without region first, and if still not converging then without baseline MADRS total score. Effect size and Number Needed to Treat (NNT) will be provided.

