Between group effect size will be defined as: Natural Log(odds ratio)xsqrt(3)/pi

The NNT will be derived as 1/Risk Reduction where Risk Reduction (RR) = (SEP-4199 trt group – placebo response rate). The NNT results will be provided in whole numbers with any fractional values rounded up to the nearest whole number.

The 95% CI will also be presented (only when the lower and upper limits are of the same sign) and are computed by taking the reciprocal of the 95% lower and upper bound of the RR. The lower confidence limit will be rounded down to the largest integer value that is less than the computed estimate, and the upper confidence limit will be rounded up to the smallest integer value that is greater than the computed estimate.

Cochran-Armitage test for trend will be used to test for association between MADRS response and the three treatments.

The log rank testing method will be used to test for differences among the treatments for time to MADRS response. ITT subjects discontinuing the study and those completing the study without meeting the criteria for MADRS response will be censored at the date of last dose of study drug or, if unknown, the end of study date. The analysis will be supplemented with Kaplan-Meier curves to illustrate the differences among the three treatments. A Cox proportional hazards model will also be used with treatment, region, and baseline value as parameters. Wald Chi-square p-value will be included.

A cumulative distribution curve for all treatment groups will be presented, plotting the cumulative percent of MADRS responders versus the percent reduction at Week 6 from baseline.

16.3.3.6. MADRS remission at Week 6

Remission incidence rate, defined as MADRS total score ≤ 12 , will be analyzed similarly to the MADRS responder analysis, including the sensitivity analysis of observed values and of assessing the removal of remote visits (see [Section 16.3.3.5](#)).

Subjects with MADRS total scores ≤ 10 and ≤ 8 at Week 6 will be summarized using descriptive statistics.

A cumulative distribution curve for all treatment groups will be presented, plotting the cumulative percent of MADRS remissions versus the MADRS total score at Week 6.

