PROC LIFETEST OUTSURV=PROBRESPONSE TIMELIST=(9 16 30 44);  
  TIME RSPTIME*RSPSTAT(1);  
  STRATA TRTPN / DIFF=CONTROL ('Placebo');  
RUN;
```

```
ODS OUTPUT HAZARDRATIOS=HAZARDRATIOS PARAMETERESTIMATES=PARAMETERESTIMATES;PROC PHREG;  
  CLASS REGION TRTP (REF='Placebo') / PARAM=REF;  
  MODEL RSPTIME*RSPSTAT(1)=TRTP REGION TOTBL;  
  HAZARDRATIO TRTP / DIFF=REF;  
  CONTRAST '200 MG VS. PLACEBO' TRTP 1 0 / ESTIMATE;  
  CONTRAST '400 MG VS. PLACEBO' TRTP 0 1 / ESTIMATE;  
RUN;
```

Document:

Author:

Version Number:

V2.0

Version Date:

21MAY2020

Template No: CS_TP_BS016 Revision 4
Effective Date: 01Apr2016

Reference: CS_WI_BS005

LOGISTIC REGRESSION

* Placebo is reference;
PROC LOGISTIC DESCENDING;
 CLASS TRTPN REGION / PARAM=REF;
 MODEL RESP = TRTPN REGION TOTBL;
 CONTRAST '200 MG vs. PLACEBO' TRTPN 1 0 / ESTIMATE=EXP;
 CONTRAST '400 MG vs. PLACEBO' TRTPN 0 1 / ESTIMATE=EXP;
 CONTRAST '200 MG vs. 400 MG' TRTPN -1 1 / ESTIMATE=EXP;
CONTRAST '(200 MG + 400 MG) vs Placebo' TRTPN 0.5 0.5 / ESTIMATE=EXP;RUN;

COCHRAN-ARMITAGE TEST

```
PROC FREQ;  
    TABLE TRTP*RESP/CMH TREND;  
RUN;
```

MULTIPLICITY-ADJUSTED P-VALUES

*Example raw p-values;
DATA STUDY;
 INPUT HYP \$ FAMILY PARALLEL \$ SERIAL \$ RAWP;
 DATALINES;
 H1 1 0000 0000 0.1403
 H2 1 0000 0000 0.0095
 H3 2 0000 1000 0.0559
 H4 2 0000 0100 0.0051
 ;
RUN;

%TREEGATE(TEST=HOCHBERG, GAMMA=0.9);

Document:

Author:

Version Number:
Version Date:

V2.0
21MAY2020

Template No: CS_TP_BS016 Revision 4
Effective Date: 01Apr2016

Reference: CS_WI_BS005

PATTERN MIXTURE MODEL (PMM) WITH PLACEBO BASED MI

The steps to implement this sensitivity analysis are as follows. For Japan cohort analysis, code must be adapted by removing REGION variable.

Step 1: Intermittent missing MADRS total scores will be imputed for each treatment using non-missing data from all ITT subjects within the treatment group by a Markov Chain Monte Carlo (MCMC) imputation model which assumes a multivariate normal distribution over all variables included in the imputation model. This imputation is based on the MAR assumption, ie, the missing data are assumed to follow the same model as the other patients in their respective treatment group.

```
PROC MI DATA=xxx OUT=yyy NIMPUTE=1000 SEED=12345 MINIMUM=. . 0 0 0 0 MAXIMUM=. . 60 60 60 60  
MINMAXITER=100;  
    BY TRTP;  
    VAR REGION MADRS_BASE MADRS_Wk1 MADRS_Wk2 MADRS_Wk4 MADRS_Wk6;  
    MCMC CHAIN=MULTIPLE IMPUTE=MONOTONE NBITER=5000 NITER=200;  
RUN;
```

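### The mania analysis has no valid pairwise test for an arm with no cases: those contrasts get an odds ratio of infinity or zero and a Wald p near 1, and the stated fallback cannot repair this

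*SAP*

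**What the plan says.** Protocol 15.3.6.2 states "Mania incidence rates will be analyzed similarly to the MADRS responder analysis", and SAP 17.6.1 repeats this for the safety population: "Mania incidence rates will be analyzed for the SAF population similarly to the MADRS responder analysis". A subject counts as a case with a YMRS total of 16 or more at two consecutive visits or at the last assessment, or with an adverse event of mania or hypomania.

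The method borrowed is in SAP 16.3.3.5: "The MADRS total score responder proportions at Week 6 will be compared among the 3 treatment groups using logistic regression", with treatment, region and baseline MADRS in the model. On non-convergence, "the model will be attempted without region first, and if still not converging then without baseline MADRS total score". No further step is given.

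The logistic code in SAP Appendix 3 is "MODEL RESP = TRTPN REGION TOTBL" with contrasts such as "CONTRAST '200 MG vs. PLACEBO' TRTPN 1 0 / ESTIMATE=EXP". It has no Firth option, no exact statement and no rule for sparse events. The same section adds an effect size of ln(OR) × √3/π, an NNT defined as the reciprocal of the risk difference, and a trend test: "Cochran-Armitage test for trend will be used to test for association between MADRS response and the three treatments".

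SAP 16.3.3.3 does limit reporting to counts and percentages when numbers are too small, but only for the SDS day-count composites. SAP 17 makes between-group safety testing the exception, and 17.6.1 invokes that exception for mania.

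**The concern.** The responder model suits a common outcome. Mania may be rare here: treatment lasts six weeks, Protocol 8.1 requires a YMRS total of 12 or less at screening, and a case identified by YMRS needs 16 or more. If one arm has no cases, the likelihood keeps rising as that arm's log-odds falls without limit, so the treatment coefficient has no finite maximum. Region and baseline are not the cause, so removing them does not help.

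Mania is the first safety endpoint listed in both documents. The pattern that matters most clinically is a clean placebo arm with cases on both doses. In that pattern both planned dose-versus-placebo tests fail, and any replacement would be chosen after unblinding.

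**Working it through.** **Inputs.** Arm size is 98 (SAP 3.1; it follows from 93 evaluable plus about 5%: 93/0.95 = 97.9). Tests are two-sided at 0.05 (SAP 6.6). The model and fallback are as above. The documents state no mania rate, case count or power for mania, so there is no figure of the plan's own to reproduce. The counts below are illustrations, written placebo/200 mg/400 mg.

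**Step 1: the planned test at 0/8/8.** Newton iterations of the logistic model with treatment only, 200 mg versus placebo:

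| Iterations | Log odds ratio | SE | Wald p |
|---|---|---|---|
| 8 | 6.78 | 10.1 | 0.50 |
| 15 | 13.78 | 333 | 0.97 |
| 18 | 16.78 | 1,494 | 0.991 |
| 20 | 18.78 | 4,060 | 0.996 |

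Each iteration adds about 1 to the estimate and multiplies its SE by about 1.65, so estimate/SE tends to 0 and p to 1. The p-value reflects the stopping rule. A relative-gradient stop of 1e-8 (assumed) ends at iteration 18. That stop is reached without a convergence failure, so the fallback might not even be triggered.

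**Step 2: does dropping covariates help?** With simulated region and baseline in the model, Wald p at 0/8/8 is 0.991. Without them it is 0.991.

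**Step 3: comparison with methods that tolerate zero cells.** The Firth values are unadjusted; the odds ratio then equals adding 0.5 to each cell. For 8 versus 0 it is (8.5/90.5)/(0.5/98.5) = 18.5.

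| Counts | Contrast | Wald p (planned model) | Fisher p | Firth OR, p |
|---|---|---|---|---|
| 0/5/5 | either dose v placebo | 0.994 | 0.059 | 11.6, 0.025 |
| 0/8/8 | either dose v placebo | 0.991 | 0.0067 | 18.5, 0.003 |
| 0/12/15 | 200 mg v placebo | 0.991 | 0.0003 | 28.5, 0.0001 |
| 8/0/8 | 200 mg v placebo | 0.991 | 0.0067 | 0.05, 0.003 |

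At 8/0/8 the fitted odds ratio for 200 mg goes to 0 (about 5e-08).

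**Step 4: what survives.**
- *Contrasts between non-empty arms.* At 3/4/0 the 200 mg odds ratio is 1.35 with p 0.70. Whichever single arm is empty, one of the four coded contrasts survives and three fail.
- *NNT.* For 8/98 versus 0/98 it is 98/8 = 12.25, reported as 13.
- *Trend test, scores 0, 1, 2.* At 0/8/8 the expected count per arm is 16/3 = 5.33. T = 1 × 2.67 + 2 × 2.67 = 8.0; variance = (16/294)(278/294) × 98 × 2 = 10.09; z = 2.52; p = 0.012. At 8/0/8, T = 1 × (−5.33) + 2 × 2.67 = 0, so p = 1.00.

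**Step 5: how often an arm is empty.** For an assumed common rate q, P(given arm empty) = (1−q)^98 and P(at least one of three) = 1 − [1 − (1−q)^98]³.

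| q | One given arm | At least one arm |
|---|---|---|
| 0.5% | 61% | 94% |
| 1% | 37% | 75% |
| 2% | 14% | 36% |
| 3% | 5% | 14% |
| 5% | 0.7% | 2% |

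**Step 6: how often the verdict would change.** Fisher p against an empty arm of 98 is 0.25 for 3 cases, 0.059 for 5 and 0.029 for 6. So Fisher needs 6 versus 0; Firth reaches 0.025 at 5 versus 0. With assumed true rates of 1% on placebo and 5% on a dose, P(0 versus 6 or more) for that dose is about 14%. With 1% and 3% it is about 3%.

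**The case against.** The strongest case on the other side is that little depends on this p-value. Mania is outside the multiplicity hierarchy in SAP 7.4, and no stated decision rests on it. Counts and percentages by arm are required, YMRS change is also analysed by MMRM and ANCOVA, and the trend test works when placebo is empty. The NNT already supplies a pairwise absolute measure. The case definition is broad, and Protocol 8.1 admits rapid cyclers, so the rate may be high enough to make an empty arm unlikely. Finally, similarly need not mean identically, and the SDS small-count convention could be extended.

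Most of this stands and limits the size of the point. It does not remove it: 17.6.1 specifies a pairwise comparison that cannot function with an empty arm, and the surviving trend test does not replace it (8/0/8 gives p 1.00).

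A reader might infer that any empty arm ruins the whole mania analysis, NNT included. The documents do not support that. An empty dose arm leaves the other dose's comparison with placebo intact, and the NNT in SAP 16.3.3.5 does not use the logistic fit. A reader might also take the empty-arm probabilities as the chance of a wrong conclusion. They are not: they include cases such as 3 versus 0, where Fisher's test is also non-significant.

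**Conclusion.** The point holds in a limited form. For any contrast involving an arm with no mania cases, the planned odds ratio, log-odds effect size and Wald p are uninformative, and the stated fallback cannot repair them. This follows from the model and code and needs no assumption about rates.

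How often it occurs depends on a mania rate the documents do not give: likely at about 1%, plausible at 2% to 3%, rare at 5%. The significance verdict is affected only at imbalances of about 6 versus 0 or more (5 versus 0 by the penalised test). Below that, the loss is a usable estimate and interval, not a changed conclusion. The matter should be corrected because this is a pre-specified safety comparison, but it does not touch the primary analysis or its error rate.

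**What to change.** In SAP 17.6.1 and Appendix 3, replace the reference to the responder model for mania with its own specification:

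- Firth-penalised logistic regression with treatment, plus region if estimable, used whatever the event counts or convergence messages.
- For each dose versus placebo: the odds ratio, a profile-likelihood 95% CI and a penalised likelihood-ratio p-value.
- In support: Fisher's exact p-value and an exact 95% CI for the risk difference.
- Keep the counts and percentages, NNT and trend test. Compute the effect size from the penalised odds ratio; at 8 versus 0 it is ln(18.5) × √3/π = 1.61, which is finite.

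This also settles which covariates apply. At present 17.6.1 does not say whether the carried-over baseline is MADRS or YMRS.

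The cost is a short SAP insertion and one more procedure option, with slightly shrunken odds ratios. Extending the SDS counts-and-percentages rule to mania would be a minimum alternative, but it would give up the pairwise comparison.

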17.6.2. COLUMBIA SUICIDE SEVERITY RATING SCALE (C-SSRS)

The C-SSRS is a tool designed to systematically assess and track suicidal behavior and suicidal ideation for life time, past 3 months (90 days) prior to the screening visit, and throughout the study. The strength of this suicide classification system is in its ability to comprehensively identify suicidal events while limiting the over-identification of suicidal behavior. The C-SSRS Baseline/Screening Version is used at the screening visit and the C-SSRS Since Last Visit Version is used from Visit 2 (lead-in) onward. Subjects with Type 4 (active suicidal ideation with some intent to act, without specific plan) or Type 5 (active suicidal ideation with specific plan and intent) suicidal ideation during the study will be discontinued from the study and referred to a mental health professional. C-SSRS is assessed at Visit 1/Screening, Visit 2/Baseline/Week 0, Visit 3/Week 1, Visit 4/Week 2, Visit 5/Week 4, Visit 6/Week 6, and Visit 7/Follow-up/Week 7.

C-SSRS includes four sections: Suicidal Ideation, Intensity of Ideation, Suicidal Behavior, and Answer for Actual Suicide Attempts.

The following outcomes are C-SSRS categories and have binary responses (yes/no). The categories are re-ordered from the scale to facilitate the definitions of the C-SSRS endpoints, and to provide clarity in the presentation of the results.

Suicidal ideation is measured by 5 categories, representing 5 subtypes of suicidal ideation with increasing severity:

Document:

Author:

Version Number:

V2.0

Version Date:

21MAY2020

Template No: CS_TP_BS016 Revision 4
Effective Date: 01Apr2016

Reference: CS_WI_BS005

- Category 1: Wish to be Dead
- Category 2: Non-specific Active Suicidal Thoughts
- Category 3: Active Suicidal Ideation with Any Methods (Not Plan) without Intent to Act
- Category 4: Active Suicidal Ideation with Some Intent to Act, without Specific Plan
- Category 5: Active Suicidal Ideation with Specific Plan and Intent

Suicidal behavior is measured by 5 categories, representing 5 subtypes of suicidal behavior:

- Category 6: Preparatory Acts or Behavior
- Category 7: Aborted Attempt
- Category 8: Interrupted Attempt
- Category 9: Actual Attempt (non-fatal)
- Category 10: Completed Suicide

The 10 categories above are not mutually exclusive. Subjects will be counted in each category for which they have an event.

Self-injurious behavior without suicidal intent is a non-suicide-related C-SSRS outcome, and also has a binary response (yes/no).

For the purpose of C-SSRS analysis, “baseline” and “postbaseline” are defined as follows.

Time point	Study Visit	C-SSRS Version	Derivation Rule
Baseline	Screening/Visit 1	Baseline/Screening – Past 3 Months	Most severe outcome
	Visit 2/Baseline*	Since Last Visit	
Post-baseline	All postbaseline visits up to and including Visit 6/Week 6 and Visit 7/follow-up visit, including unscheduled visits	Since Last Visit	Most severe outcome

* Note: The Visit 2/Baseline C-SSRS assessment must be administered prior to the first dose of study medication in order to be used in the C-SSRS Baseline derivation.

C-SSRS composite endpoints will be derived for each time point of interest (ie, baseline, postbaseline, and each study visit) as follows:

Document:

Author:

Version Number:

V2.0

Version Date:

21MAY2020

Template No: CS_TP_BS016 Revision 4
 Effective Date: 01Apr2016

Reference: CS_WI_BS005

- Any suicidal ideation: A “yes” answer to any one of the 5 suicidal ideation questions on C-SSRS (Categories 1-5).
- Any suicidal behavior: A “yes” answer to any one of the 5 suicidal behavior questions on the C-SSRS (Categories 6-10).
- Any Suicidal Ideation or Behavior: A “yes” answer to any one of the 10 suicidal ideation and behavior questions on the C-SSRS (Categories 1-10).

For each subject, the suicidal ideation score at each time point of interest (ie, baseline, postbaseline, each study visit including follow-up visit) is defined as the maximum suicidal ideation category (1-5) present for the time of interest. If no ideation is present a score of 0 is assigned. A suicidal ideation score of 4 or 5 is considered serious.

Intensity of ideation for the most severe ideation subtype is measured in terms of frequency, duration, controllability, deterrents, and reasons for ideation. Each is measured with responses ranging from 1 to 5 for frequency and duration, and from 0 to 5 for controllability, deterrents, and reasons for ideation. The ideation intensity total score is the sum of responses to the five items and can range from 2 to 25 for subjects with endorsed suicidal ideation. If one or more of these five items are missing at an assessment, the total score will be set to missing. If a subject did not endorse any suicidal ideation, a score of 0 for the ideation intensity total score will be given.

The number and percentage of subjects with any suicidality, any suicidal ideation, and any suicidal behavior in the SAF population will be presented for:

- Baseline (as defined above)
- Postbaseline (as defined above)
- Each scheduled study visit: Screening (lifetime; past 3 months), Visit 2/Baseline/Week 0, Visit 3/Week 1, Visit 4/Week 2, Visit 5/Week 4, Visit 6/Week 6, and Visit 7/Follow-up/Week 7.

Responses to each question will be listed.

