 - Subjects with fasting blood glucose at screening ≥ 126 mg/dL (7.0 mmol/L) will be excluded from the study.
 - Subjects with fasting blood glucose from 100-125 mg/dL (5.6-6.9 mmol/L) may enter the study based on the approval of the Medical Monitor.
 - Subjects who are found to have been non-fasting at Screening may be allowed if their blood glucose is < 200 mg/dL. Subjects with random (nonfasting) blood glucose at screening ≥ 200 mg/dL (11.1 mmol/L) must be retested in a fasted state.
 - Subjects with $\text{HbA}_{1c} > 7.0\%$ will be excluded.
16. Subject has a prolactin concentration > 100 ng/mL at screening or have a history of pituitary adenoma.
17. Subject has a body mass index (BMI) ≥ 40 or < 18 kg/m² at Screening.
18. Subject has a history of non-response to an adequate (6-week) trial of three or more antidepressants (with or without mood stabilizers) during the current episode.
19. Subject is considered by the Investigator to be at imminent risk of suicide or injury to self, others, or answers “yes” to “Suicidal Ideation” item 4 (active suicidal ideation with some intent to act, without specific plan) or item 5 (active suicidal ideation with specific plan and intent) on the C-SSRS assessment at the Screening visit (in the past month [30 days]) or Baseline.
20. Subject tests positive for drugs of abuse at screening or baseline. In the event a subject tests positive for cannabinoids (tetrahydrocannabinol), the investigator will evaluate the subject’s ability to abstain from cannabis during the study. This information will be discussed with the Medical Monitor for study enrollment consideration.
21. Subject has a history of hypersensitivity to more than two distinct chemical classes of drug (eg, sulfas and penicillins).
22. Subjects have received depot neuroleptics unless the last injection was at least one treatment cycle before randomization.
23. Subject requires treatment with a drug that consistently prolongs the QTc interval (see [Section 23](#), Appendix IV).
24. Subject has received ECT within 90 days prior to randomization or is expected to require ECT during the study course.
25. Subject is currently participating, or has participated in a study with an investigational or marketed compound or device within 6 months prior to signing the informed consent, or has participated in 3 or more studies within 18 months prior to signing the informed consent.

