15.3.6.7. Columbia-Suicide Severity Rating Scale (C-SSRS)

Frequency and severity of suicidal ideation or suicidal behavior in the C-SSRS will be summarized at each visit and overall by treatment group. Responses to each of the questions will be listed.

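### The C-SSRS tables do not count new or worsened suicidal ideation separately from ideation present at entry, and the derived severity scores feed no stated summary

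*SAP*

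**What the plan says.** The safety endpoint in Protocol Section 6.5 and SAP Section 2.6.5 is the frequency and severity of suicidal ideation and behavior on the C-SSRS. Protocol Section 15.3.6.7 repeats both parts: "Frequency and severity of suicidal ideation or suicidal behavior in the C-SSRS will be summarized at each visit and overall by treatment group".

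SAP Section 17.6.2 sets up the derivations. Baseline is the most severe outcome over the 3 months before Screening and at Visit 2. Postbaseline is the most severe outcome over all later visits, including follow-up and unscheduled visits. Any ideation means a positive answer to at least one of the five ideation questions at the time point, with no condition on baseline. The ideation score "is defined as the maximum suicidal ideation category (1-5) present for the time of interest", with 0 if there is none. "A suicidal ideation score of 4 or 5 is considered serious". An intensity total is also derived. For the ten categories, "Subjects will be counted in each category for which they have an event".

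The stated output is: "The number and percentage of subjects with any suicidality, any suicidal ideation, and any suicidal behavior in the SAF population will be presented", at baseline, postbaseline and each scheduled visit. Individual responses are listed. The section specifies no shift table, change from baseline, or count of new or worsened cases.

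**The concern.** In a bipolar depression trial, a key question for the C-SSRS is whether subjects on drug develop ideation they did not have, or move to a more severe form. Both are changes within a subject. A postbaseline percentage with any ideation combines three groups: subjects whose entry ideation persists or recurs, subjects who had it and got worse, and subjects who had none and developed it.

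The first group may well be large. On the C-SSRS, Protocol Section 8.2 excludes only positive answers to ideation items 4 or 5, together with investigator-judged imminent risk. Subjects with Categories 1 to 3 can enter.

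What is at stake is whether the report can describe emergent suicidality by arm, and whether the severity half of the endpoint has any stated output.

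**Working it through.** **Inputs.** The time points, definitions and outputs come from SAP Section 17.6.2, and the entry rule from Protocol Section 8.2. The planned 98 subjects per arm in the US and Europe come from SAP Section 3.1. The documents give no C-SSRS rates and no C-SSRS figure to reproduce, so every rate below is an assumption.

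**Step 1. Derived variables against stated outputs (SAP 17.6.2).**

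| Derived | Stated summary |
|---|---|
| Any ideation, any behavior, either | n (%) at baseline, postbaseline, each visit |
| Ten categories, counted per event | None stated; marginal counts at most |
| Ideation score, 0 to 5 | None |
| Serious class, 4 or 5 | None |
| Intensity total | None |

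**Step 2. The SAP's other safety measures.** Laboratory results have shift tables (17.2). The absolute QTc categories count values not present at baseline (17.3). AIMS has shifts, including one on maximum postbaseline severity, and worsened, unchanged or improved classes for its global score (17.6.3). BARS has the same three classes (17.6.4), and SAS has normal/abnormal shifts (17.6.5). The C-SSRS has no such comparison, and no reason is given.

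**Step 3. What two marginal counts can show.** Let N subjects have both assessments, B have ideation at baseline and P have it postbaseline. The number of new-onset cases lies between max(0, P − B) and min(P, N − B).

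- N = 98, B = 39 (40%, assumed), P = 29 (30%, assumed): from max(0, −10) = 0 to min(29, 59) = 29.
- N = 98, B = 20 (20%, assumed), P = 29: from max(0, 9) = 9 to min(29, 78) = 29.

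The planned counts do not identify the number of new cases.

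**Step 4. Worsening.** A subject going from Category 1 to Category 3 is positive for any ideation at both time points, exactly like a subject who stays at Category 1. Per-category counts, if produced, would add one to Category 3 postbaseline, but would not show that this subject had been at Category 1.

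**Step 5. Dilution, purely illustrative.** Let b be the share with baseline ideation, r the share of those in whom it persists (equal in both arms), and e the new-onset rate among the rest. Then P(any postbaseline) = b·r + (1 − b)·e. Take e = 3% on placebo and 12% on drug.

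- b = 0.20, r = 0.50: placebo 0.10 + 0.80 × 0.03 = 0.124; drug 0.10 + 0.80 × 0.12 = 0.196; risk ratio 1.58.
- b = 0.50, r = 0.70: placebo 0.35 + 0.50 × 0.03 = 0.365; drug 0.35 + 0.50 × 0.12 = 0.410; risk ratio 1.12.

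The new-onset risk ratio is 0.12 / 0.03 = 4.0 in both cases. It is also 4.0 with all subjects in the denominator, because (1 − b) cancels when b is equal across arms. No test statistic is given: SAP Section 17 plans no safety comparisons unless specified, and none is specified for the C-SSRS.

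**Step 6. Serious ideation.** Protocol Section 8.2 applies its item 4 and 5 exclusion "on the C-SSRS assessment at the Screening visit (in the past month [30 days]) or Baseline", while the analysis baseline reaches back 3 months. Under that text, a subject with Category 4 or 5 ideation 31 to 90 days before Screening can enter with a serious baseline score. The protocol synopsis gives 90 days for the same criterion, so the two passages need reconciling. Under the 30-day text, a postbaseline count of scores 4 to 5 is largely, but not strictly, emergent.

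**The case against.** The strongest reply is that nothing is hidden. The postbaseline form asks about the time since the last visit, so every new case enters the postbaseline and per-visit counts. Every response is listed, and events reported as adverse events also appear in the adverse event tables. A reader might infer that new ideation is never counted, or would be under-reported. The documents do not support that; only the separate count is absent.

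A reader might also infer bias from the time windows, since baseline covers about 3 months and postbaseline about 7 weeks. That asymmetry is the same in every arm and does not bias the comparison with placebo. Visit 2 is also tabulated on its own. The asymmetry remains in the emergent count proposed here, so it is no argument for the change.

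Movement to Category 4 or 5 would be largely visible if per-category counts are shown, and the SAP says such subjects are discontinued. The gap is therefore mainly in Categories 1 to 3.

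The protocol asks for frequency and severity and does not promise an emergent or shift analysis. The table templates mentioned in SAP Section 8 were not available and may contain more.

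These points limit the concern but do not remove it. Neither listings nor adverse event tables, which depend on spontaneous report and investigator judgment, give a within-subject comparison on the structured scale. Severity has been promised, and the variables derived to measure it have no stated use.

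**Conclusion.** The concern holds for the SAP text, as a reporting gap in Section 17.6.2. The C-SSRS is summarized only as marginal percentages, so new or worsened ideation cannot be separated from ideation present at entry. The severity variables lead to no stated table.

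The size in this trial cannot be computed from the documents. The bounds in Step 3 show that the planned counts can be consistent with very different numbers of new cases. The risk ratios of 1.12 to 1.58 against 4.0 show dilution under assumed rates only. They also assume equal persistence in both arms and a drug effect confined to subjects without baseline ideation, which favors the emergent analysis.

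This is a worthwhile, low-cost improvement. It does not touch the efficacy analyses or the validity of the planned tables.

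**What to change.** Keep the marginal tables. In SAP Section 17.6.2 add, by treatment group in the SAF population, among subjects with a baseline and at least one postbaseline C-SSRS:

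1. A shift table of maximum baseline by maximum postbaseline ideation score (0 to 5).
2. n (%) with new or worsened ideation, meaning a postbaseline score above the baseline score.
3. n (%) with emergent serious ideation (0 to 3 at baseline, 4 to 5 postbaseline), and n (%) with emergent behavior (none at baseline, any postbaseline).

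A footnote should say that the 3-month worst-case baseline makes the emergent counts conservative: ideation that had resolved before dosing and recurs at the same or a lower level is not classed as emergent. The section should also say whether the intensity total is to be summarized or only listed, since these tables do not use it.

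The cost is a few lines of SAP text and one or two descriptive tables from variables already derived. No new data and no tests are needed, and no clinical management rule changes.
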